4.4. End of Study Definition

A participant is considered to have completed the study if he/she has completed all phases of the study, including the last scheduled follow-up contact shown in the SoA.

The end of the study is defined as the date of the final follow-up contact shown in the SoA for the last participant in the trial.

5. STUDY POPULATION

This study can fulfill its objectives only if appropriate participants are enrolled. The following eligibility criteria are designed to select participants for whom participation in the study is considered appropriate. All relevant medical and nonmedical conditions should be taken into consideration when deciding whether a particular participant is suitable for this protocol.

Prospective approval of protocol deviations to recruitment and enrollment criteria, also known as protocol waivers or exemptions, is not permitted.

5.1. Inclusion Criteria

Participants are eligible to be included in the study only if all of the following criteria apply:

Age and Sex:

- 1. Healthy (except obese) female participants of non-childbearing potential and/or male participants, at the time of screening, must be 18 to 60 years of age, inclusive, at the time of signing the informed consent document (ICD).
 - Refer to Appendix 4 for reproductive criteria for male (Section 10.4.1) and female (Section 10.4.2) participants of non-child bearing potential.

Type of Participant and Disease Characteristics:

- 2. Male and female of non-child bearing potential participants, who are healthy as determined by medical evaluation including medical history, physical examination, vital assessments, 12-lead ECGs, and laboratory tests.
- 3. Participants who are willing and able to comply with all scheduled visits, treatment plan, laboratory tests, lifestyle considerations, and other study procedures.

Weight:

4. Body mass index (BMI) of 17.5 to 35 kg/m²; and a total body weight >50 kg (110 lb).

Informed Consent:

5. Capable of giving signed informed consent as described in Appendix 1, which includes compliance with the requirements and restrictions listed in the ICD and in this protocol.

5.2. Exclusion Criteria

Participants are excluded from the study if any of the following criteria apply:

Medical Conditions:

- 1. Evidence or history of clinically significant hematological, renal, endocrine, pulmonary, gastrointestinal, cardiovascular, hepatic, psychiatric, neurological, immunological/rheumatological, or allergic disease (including drug allergies, but excluding untreated, asymptomatic, seasonal allergies at the time of dosing).
- 2. Participants who have any visible skin damage or skin condition (eg sunburn, excessively deep tans, uneven skin tones, tattoos, scars, excessive hair, numerous freckles, or other disfigurations) in or around the application site which, in the opinion of the investigative personnel, will interfere with the evaluation of the test site reaction.
- 3. Participants who have a history of or have active AD/eczema/urticaria.
- 4. Evidence of active or latent or inadequately treated infection with Mycobacterium tuberculosis (TB) as defined by both of the following:
 - A positive QuantiFERON-TB Gold In-tube or equivalent test (QFT).
 - History of either untreated or inadequately treated latent or active TB infection, or current treatment for the same.
- 5. History of HIV infection, hepatitis B, or hepatitis C; positive testing for HIV, hepatitis B surface antigen (HBsAg), hepatitis B core antibody (HBcAb) or hepatitis C antibody (HCVAb). Hepatitis B vaccination is allowed. As an exception a positive HBsAb test due to hepatitis B vaccination is permissible.
- 6. Have a history of systemic infection requiring hospitalization, parenteral antimicrobial therapy, or as otherwise judged clinically significant by the investigator within 6 months prior to Day 1.
- 7. A history (single episode) of disseminated herpes zoster or disseminated herpes simplex, or a recurrent (more than one episode of) localized, dermatomal herpes zoster.

- 8. Acute disease state (unstable medical condition such as nausea, vomiting, fever or diarrhea, etc) within 7 days of Day 1.
- 9. Have any malignancies or have a history of malignancies with the exception of adequately treated or excised non-metastatic basal cell or squamous cell cancer of the skin.
- 10. Have a first-degree relative with hereditary immunodeficiency.
- 11. A history of any lymphoproliferative disorder (such as Epstein Barr Virus [EBV] related lymphoproliferative disorder), history of lymphoma, leukemia, malignancies or signs and symptoms suggestive of current lymphatic disease.
- 12. Have undergone significant trauma or major surgery within 4 weeks of screening.
- 13. Other medical or psychiatric condition including recent (within the past year) or active suicidal ideation/behavior or laboratory abnormality or other conditions or situations related to COVID-19 pandemic (eg. Contact with positive case, residence, or travel to an area with high incidence) that may increase the risk of study participation or, in the investigator's judgment, make the participant inappropriate for the study.

Prior/Concomitant Therapy:

- 14. Use of prescription or nonprescription drugs and dietary and herbal supplements within 7 days or 5 half-lives (whichever is longer) prior to the first dose of study intervention. (Refer to Section 6.8 Concomitant Therapy for additional details).
- 15. Participants who are vaccinated with vaccines that have live components (or live attenuated vaccines) within the 6 weeks prior to the first dose of PF-07295324/vehicle or PF-07259955/vehicle or who are expected to be vaccinated during treatment or during follow-up period.

NOTE regarding COVID-19 vaccines with authorization or approval for emergency use:

There is no requirement for washout of COVID-19 vaccines prior to the first dose of PF-07295324/vehicle or PF-07259955/vehicle if the vaccine is not live attenuated (eg, mRNA, utilizing a viral vector, inactivated virus). There is no protocol-specified requirement for the interruption of IP dosing prior to or after vaccination if the COVID-19 vaccine is not live attenuated.

16. Participants in any cohort of this study can only be randomized **and** receive the IP in only 1 cohort of this study.
Prior/Concurrent Clinical Study Experience:

17. Previous administration with an investigational drug within 30 days (or as determined by the local requirement) or 5 half-lives preceding the first dose of study intervention used in this study (whichever is longer).

Diagnostic Assessments:

- 18. A positive urine drug test.
- 19. Screening supine BP ≥140 mm Hg (systolic) or ≥90 mm Hg (diastolic), following at least 5 minutes of supine rest. If BP is ≥140 mm Hg (systolic) or ≥90 mm Hg (diastolic), the BP should be repeated 2 more times and the average of the 3 BP values should be used to determine the participant's eligibility.
- 20. Baseline 12-lead electrocardiogram (ECG) that demonstrates clinically relevant abnormalities that may affect participant safety or interpretation of study results (eg, baseline QTcF interval >450 msec, complete left bundle branch block [LBBB], signs of an acute or indeterminate-age myocardial infarction, ST-T interval changes suggestive of myocardial ischemia, second- or third-degree atrioventricular [AV] block, or serious bradyarrhythmias or tachyarrhythmias). If the baseline uncorrected QT interval is >450 msec, this interval should be rate-corrected using the Fridericia method and the resulting QTcF should be used for decision making and reporting. If QTcF exceeds 450 msec, or QRS exceeds 120 msec, the ECG should be used to determine the participant's eligibility. Computer-interpreted ECGs should be overread by a physician experienced in reading ECGs before excluding participants.
- 21. Participants with ANY of the following abnormalities in clinical laboratory tests at screening, as assessed by the study-specific laboratory and confirmed by a single repeat test, if deemed necessary:
 - Aspartate aminotransferase (AST) or alanine aminotransferase (ALT) level ≥1.5 × upper limit of normal (ULN);
 - Total bilirubin level $\geq 1.5 \times ULN$; participants with a history of Gilbert's syndrome may have direct bilirubin measured and would be eligible for this study provided the direct bilirubin level is $\leq ULN$.

Other Exclusions:

22. History of alcohol abuse or binge drinking and/or any other illicit drug use or dependence within 6 months of Screening. Binge drinking is defined as a pattern of 5 (male) and 4 (female) or more alcoholic drinks in about 2 hours. As a general rule, alcohol intake should not exceed 14 units per week (1 unit = 8 ounces (240 mL) beer, 1 ounce (30 mL) of 40% spirit or 3 ounces (90 mL) of wine).

- 23. Use of tobacco/nicotine containing products more than 5 cigarettes/day.
- 24. Blood donation (excluding plasma donations) of approximately 1 pint (500 mL) or more within 60 days prior to dosing.
- 25. History of serious adverse reactions or hypersensitivity to any topical drug; or known allergy to any of the test product(s) or any components in the test product(s) or history of hypersensitivity; or allergic reactions to any of the study preparations as described in the PF-07295324 IB and PF-07259955 IB.
- 26. Not willing to refrain from shaving, the use of depilatories or other hair-removal activities, antiperspirants, lotions, skin creams, fragrances or perfumes, or body oils (eg, baby oil; coconut oil), use of hair products, hair gels, and hair oil in the treatment areas for 48 hours prior to admission to the CRU and for the duration of the stay in the CRU.
- 27. Unwilling or unable to comply with the criteria in the Lifestyle Considerations section of this protocol.
- 28. Investigator site staff or Pfizer employees directly involved in the conduct of the study, site staff otherwise supervised by the investigator, and their respective family members.

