7.1.1. ECG Changes

A participant who meets either of the bulleted criterion based on the average of triplicate ECG readings will be withdrawn from the study.

- QTcF > 500 msec.
- Change from baseline: QTcF >60 msec.

If a clinically significant finding is identified (including, but not limited to, changes from baseline in QTcF after enrollment), the investigator or qualified designee will determine if the participant can continue in the study and if any change in participant management is needed. This review of the ECG printed at the time of collection must be documented. Any new clinically relevant finding should be reported as an AE.

See the SoA for data to be collected at the time of intervention discontinuation and follow-up and for any further evaluations that need to be completed.

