10.2. Appendix 2: Clinical Laboratory Tests

The following safety laboratory tests will be performed at times defined in the SoA section of this protocol. Additional laboratory results may be reported on these samples as a result of the method of analysis or the type of analyzer used by the clinical laboratory; or as derived from calculated values. These additional tests would not require additional collection of blood. Unscheduled clinical laboratory measurements may be obtained at any time during the study to assess any perceived safety concerns.

Hematology	Chemistry	Urinalysis	Other
Hemoglobin Hematocrit RBC count MCV MCH MCHC Platelet count WBC count Total neutrophils (Abs) Eosinophils (Abs) Monocytes (Abs) Basophils (Abs) Lymphocytes (Abs) Reticulocytes (Abs)	BUN/urea and creatinine Glucose (fasting) Calcium Sodium Potassium Chloride Total CO ₂ (bicarbonate) AST, ALT Total bilirubin Alkaline phosphatase Uric acid Albumin Total protein	pH Glucose (qual) Protein (qual) Blood (qual) Ketones Nitrites Leukocyte esterase Urobilinogen Urine bilirubin Microscopy ^a	 COVID-19 testing Urine drug screening^b At screening only: FSH^c Hepatitis B surface antigen Hepatitis B core antibody Hepatitis C antibody TB testing Human immunodeficiency virus

 Table 7.
 Protocol Required Safety Laboratory Assessments

a. Only if urine dipstick is positive for blood, protein, nitrites, or leukocyte esterase.

b. The minimum requirement for drug screening includes cocaine, tetrahydrocannabinol (THC), opiates/opioids, benzodiazepines, and amphetamines (others are site and study specific).

c. For confirmation of postmenopausal status only.

The investigator must review the laboratory report, document this review, and record any clinically relevant changes occurring during the study in the AE section of the CRF.

Investigators must document their review of each laboratory safety report.

Laboratory/analyte results that could unblind the study will not be reported to investigator sites or other blinded personnel until the study has been unblinded.

Any remaining serum/plasma from samples collected for clinical safety laboratory measurements at baseline and at all times after dose application may be retained and stored for the duration of the study.

10.3. Appendix **3:** Adverse Events: Definitions and Procedures for Recording, Evaluating, Follow-Up, and Reporting

temporally associated with the use of study intervention.

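### Exclusion criterion 4 names active, latent or inadequately treated TB, but its two-part definition, read literally, misses two of the groups it names

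*Protocol*

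**What the plan says.** Protocol Section 5.2 opens its list with "Participants are excluded from the study if any of the following criteria apply", so each numbered criterion is sufficient by itself. Criterion 4 then reads "Evidence of active or latent or inadequately treated infection with Mycobacterium tuberculosis (TB) as defined by both of the following", followed by two bullets:

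- a positive QuantiFERON-TB Gold test or equivalent (QFT);
- "History of either untreated or inadequately treated latent or active TB infection, or current treatment for the same".

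The Schedule of Activities (Section 1.3.1, Table 1) places the QFT at screening. Appendix 2 lists TB testing among the screening-only tests in Table 7, titled "Protocol Required Safety Laboratory Assessments". Neither place says what follows from a positive result. Section 5 does not allow recruitment or enrolment criteria to be waived in advance. The SAP does not deal with eligibility.

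**The concern.** The definition is narrower than the condition it is meant to define. The opening words of criterion 4 read as a firm exclusion of anyone with active, latent or inadequately treated TB. The connector then requires two findings together, and some volunteers in the named groups will have only one of them.

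Every volunteer has a QFT at screening. The criterion does not settle what a positive result means without a known TB history, or what a known history means when the test is negative. One reader could apply the opening words and another the definition, and reach opposite decisions on the same volunteer. This is a participant-safety matter in the first human study of two JAK inhibitors. The protocol itself names the immune and hematolymphopoietic systems as target organs in the rat oral studies of both compounds (Sections 2.2.3.1 and 2.2.3.2).

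**Working it through.** No sample size, power or error rate is involved. The check is on the logic of the criterion, followed by a search for any other rule that closes the gap.

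**Step 1. The literal rule.** Let Q be a positive QFT (first bullet) and H the second bullet: an untreated or inadequately treated TB history, or current treatment. The rule is: criterion 4 is met if Q AND H.

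| QFT | History or current treatment | Criterion 4 met? | Named in the opening words? |
|---|---|---|---|
| + | yes | yes | yes |
| + | no: newly found latent infection, no known TB history | **no** | yes (latent) – group (a) |
| − | yes: untreated or inadequately treated, off treatment | **no** | yes – group (b) |
| − | yes: on current treatment | no | generally caught by criterion 14 (recent drug use) |
| − | no | no | no |

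Of the four combinations of Q and H, only Q+H+ meets the criterion. A QFT-positive volunteer with adequately treated past TB is not counted in group (a), because the opening words do not name that case.

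**Step 2. Does *both* mean AND in this protocol?** The protocol marks alternatives when one item is enough:

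- Section 5.2 uses *any* for the whole list: "Participants are excluded from the study if any of the following criteria apply".
- Criterion 21 places a capitalised *any* before "of the following abnormalities in clinical laboratory tests at screening, as assessed by the study-specific laboratory and confirmed by a single repeat test".
- Section 7.1.1 uses *either* for two bullets: "A participant who meets either of the bulleted criterion based on the average of triplicate ECG readings will be withdrawn from the study".
- Criterion 5, directly after criterion 4, lists history of HIV or hepatitis and positive testing as separate grounds, with no *both*.

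Against that usage, *both* is most naturally read as requiring the two items together.

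**Step 3. Does another provision close the gap?**

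- Criterion 1 covers clinically significant pulmonary disease. It would not reach symptom-free latent infection found only by the QFT.
- Criterion 6 covers certain systemic infections in the 6 months before Day 1.
- Criterion 13 covers other conditions or laboratory abnormalities that may raise risk or that the investigator judges unsuitable.
- Criterion 14 would generally catch current TB drugs, but not past infection in someone off treatment.
- Inclusion 2 requires volunteers to be "healthy as determined by medical evaluation including medical history, physical examination, vital assessments, 12-lead ECGs, and laboratory tests", and TB testing is among the required laboratory tests.
- Section 5 asks that all relevant conditions be weighed when judging suitability.
- Criterion 21 sets laboratory cut-offs, but only for AST/ALT and bilirubin.

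Several of these could keep out a volunteer in group (a) or (b). None is an explicit TB or QFT rule, and most rest on judgment.

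**Step 4. Scale.** Section 1.1 and Section 9.5 give about 6 participants per cohort, randomized 4 active to 2 vehicle.

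- Planned cohorts: 2 × 6 = 12 participants, of whom 2 × 4 = 8 on active.
- With both optional cohorts: 4 × 6 = 24 participants, of whom 4 × 4 = 16 on active.

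The documents give no prevalence of TB or of positive QFT, so no expected number in group (a) or (b) can be stated.

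**The case against.** The strongest reply is that this is unclear drafting and not an open door. Inclusion 2 is mandatory and rests on medical history and laboratory tests that include TB testing. Criterion 13 expressly covers laboratory abnormalities, so an unexplained positive QFT has a direct route to exclusion. The study runs in the sponsor's own clinical research unit with few volunteers, so uneven handling is less likely than at many sites. The risk table in Section 2.3.1 does not list TB or opportunistic infection. Projected unbound exposures are about 18-fold and 3.7-fold below the IFNγ IC50 for PF-07295324 and PF-07259955 (Sections 4.3.1 and 4.3.2).

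Each group also has an alternative reading. A new positive QFT in a never-treated volunteer might itself be taken as a history of untreated latent infection, which would bring group (a) under the second bullet. For group (b), one could argue that the first bullet supplies the evidence of infection and the second only the treatment status, so that a QFT-negative volunteer never falls under the opening words.

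The points on small practical effect and on general back-stops stand. They bear on consequence and do not make the definition match what it defines. The reading that rescues group (a) is not stated in the text, and it would leave group (b) uncovered. The narrow reading for group (b) does not succeed, because inadequately treated infection is named in the opening words themselves. If two separate definitions were intended, the rewording is still needed, because the text does not say so.

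**Conclusion.** The concern holds. Criterion 4 is internally inconsistent: followed as written, it leaves out two groups that its own opening words include, and no other explicit TB or QFT rule in the Protocol or SAP covers them. It should be fixed, because it is a stated safety criterion that gives a result at odds with its own terms.

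The practical effect is small. Enrolment is about 12 to 24, dosing is topical and inpatient for 10 days, general provisions may catch individual cases, and no endpoint, sample size or analysis changes. The conclusion rests on reading *both* as AND, which the protocol's usage elsewhere supports, and on not treating a new positive QFT as a history. If it were so treated, only group (b) would remain. The documents do not show which rule was intended.

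**What to change.** Reconcile the opening words, the connector and the two bullets of criterion 4 so that all describe the same group of volunteers. Whether the definition is widened to match the opening words, or the opening words narrowed to match the definition, is for the sponsor to decide. As a secondary clarification, the same edit could state how a QFT-positive volunteer with adequately treated past TB is handled, since the opening words do not name that case.

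The cost is one reworded criterion in an amendment. No added test or visit is needed. If the definition is widened, there may be a few more screen failures.

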5.3. Lifestyle Considerations

The following guidelines are provided:

5.3.1. Meals and Dietary Restrictions

- Participants must abstain from all food and drink (except water) at least at least 4 hours prior to any safety laboratory evaluations conducted at pre-AM application.
- Otherwise, water, meals, and snacks may be consumed without restriction.

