1.3. Schedule of Activities

The SoA table provides an overview of the protocol visits and procedures. Refer to the STUDY ASSESSMENTS AND PROCEDURES section of the protocol for detailed information on each procedure and assessment required for compliance with the protocol.

The investigator may schedule visits (unplanned visits) in addition to those listed in the SoA table, in order to conduct evaluations or assessments required to protect the well-being of the participant.

1.3.1. Schedule of Activities from Screening to End of Study (EOS): Multiple doses of topical application for 10 days

Visit Identifier ^a	Screening		In patient										Follow-Up Contact/EOS	Early Termination/ Discontinuation
Days Relative to Day 1	≤-28	Day -1	1	2	3-4	5	6	7	8-9	10	11	12 ^b	41±3°	
Informed consent	Х													
Outpatient visit to CRU	Х													
Inclusion/exclusion criteria	Х	Х												
CRU confinement ^d		Х	\rightarrow	Х										
Medical/medication history (update) ^e	Х	Х												
Physical exam ^f	Х	Х										Х		Х
Demography (including height and weight)	Х													
Contraception check	Х	Х										Х	Х	Х
Urine drug testing	Х	Х												
COVID-19 testing ^g	Х	Х												
COVID-19 temperature check	Х	Х												
Triplicate supine 12-Lead ECG ^h (single at screening and ET)	Х		Х	Х		Х		Х		Х	Х	Х		Х
Supine Vital signs ⁱ (Blood pressure and pulse rate)	Х		Х	Х		Х		Х		Х	Х	Х		Х
Topical administration of study intervention, Q12H ^j			X	X	Х	Х	Х	X	X	X				
Serious and non-serious adverse event monitoring	Х	Х	\rightarrow	Х	Х	Х								

Table 1.	Schedule of Activitie	s from Screening to	End of Study
		0	· ·

Visit Identifier ^a	Screening						In pati		Follow-Up Contact/EOS	Early Termination/ Discontinuation				
Days Relative to Day 1	≤-28	Day -1	1	2	3-4	5	6	7	8-9	10	11	12 ^b	41±3°	
Application site monitoring ^k	X	Х	\rightarrow	\rightarrow	\rightarrow	Х		Х						
Serum FSH ¹	Х													
QuantiFERON TB Gold Test or equivalent	Х													
HIV, HCVAb, HBcAb, HBsAg	X													
Safety Laboratory ^m	X	Х				Х		X		X		Х		Х
Pharmacokinetic blood sampling ⁿ			Х	Х		Х		X		X	Х	Х		Х
CC														

Table 1. Schedule of Activities from Screening to End of Study

a. Day relative to start of study intervention (D1). Abbreviations used in this table may be found in Appendix 9.

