- b. Participants will be discharged on D12, following completion of all scheduled procedures. Participants who may experience AEs or dermatological observations on D12 may be confined to the CRU at the discretion of the PI until AEs or dermatological observations are resolved and may be asked to return to the CRU at the discretion of the investigator, for follow-up contact. If unexpected reactions (eg, rash, hives) other than irritation reactions outlined in, Section 8.2.5 occur, the body surface area location must be recorded. Appearance of the reactions should be described.
- c. Participants will be scheduled for a follow-up phone call on D41±3 days. Additional follow-up contacts may be scheduled at investigator's discretion, including follow-ups to monitor open AEs based on emerging safety data.
- d. Participants will be admitted at least 12 hours prior to dosing.
- e. Medical history will be collected at screening and updated on D-1 only.
- f. Complete physical examination will be conducted at screening or on D-1 only; otherwise brief physical examination is envisioned for findings during previous or new/open AEs, at the discretion of the PI.
- g. Check for exposure to COVID-19 positive participants as per standard CRU protocol.
- h. Singlet measure at screening and early termination only. Triplicate measures at all other times approximately 2-4 minutes apart; ECGs will be measured on D1 and D10 as specified in Table 2; ECGs will be measured at pre-AM application on D2, D5 and D7, on D11 at approximately 24H post last application and on D12 prior to discharge.
- i. Vitals will be collected at screening and early termination; vitals should be measured on D1 and D10 as specified in Table 2; vitals should be collected at pre- AM application on D2, D5 and D7; vital signs will be collected on D11 at approximately 24H post last application and D12 prior to discharge.

Table 1. Schedule of Activities from Screening to End of Study

Visit Identifier ^a	Screening		In patient									Follow-Up Contact/EOS	Early Termination/ Discontinuation	
Days Relative to Day 1	≤-28	Day -1	1	2	3-4	5	6	7	8-9	10	11	12 ^b	41±3°	

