j. In Cohorts 1 and 2, study intervention/vehicle will be applied, on D1 to D9, Q12H. PM dose will be applied approximately 12±1 hours post-AM dose. On D10, study intervention/vehicle will be applied, at AM only. No PM dose will be applied on D10. PF-07295324/vehicle ointment will be applied to participants enrolled in Cohort 1 and in optional Cohort 3. PF-07259955/vehicle cream, will be applied to participants enrolled in Cohort 2. PF-07295324 or PF-07259955 may be studied in optional Cohort 4.

- k. Application sites will be identified at screening. Examination of application sites will be conducted at screening and on D-1. On D1 to D10, skin irritation assessment using Draize's scoring (Table 5) will be performed prior to each application of the investigational product. On D11 (approximately 24H post last dose) and on D12 prior to discharge, skin irritation assessment using Draize's scoring will be performed. Refer to Section 8.2.5.
- 1. At screening, FSH test will be performed in females only, to confirm postmenopausal status.
- m. Safety labs will be collected at screening, admission (D-1), during in-patient dosing as specified in Table 1, at discharge, and at early termination.
- n. See Table 2 for detailed blood sampling schedule for PK on D1 and D10. Samples will be collected at pre-AM application on D2, D5 and D7. PK sample will be collected on D12, prior to discharge.

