3.1.2. Laboratory Data

Safety laboratory tests will be performed as described in the protocol. See Protocol Appendix 2 for the list of clinical safety laboratory tests to be performed.

To determine if there are any clinically significant laboratory abnormalities, the hematological, clinical chemistry (serum) and urinalysis safety tests will be assessed against the criteria specified in the sponsor reporting standards. The assessment will not take into account whether each subject's baseline test result is within or outside the laboratory reference range for the particular laboratory parameter.

Baseline of safety laboratory tests is defined as the pre-dose measurement on Day -1. If a value is missing on Day -1, then the last pre-dose measurement will be used as baseline.

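### The fasting rule does not reach the Day -1 baseline or the Day 12 sample of a glucose test that the protocol labels as fasting, so comparisons with baseline may mix fed and fasted values

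*Protocol*

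**What the plan says.** Four places bear on this.

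- **The test.** Protocol Appendix 2, Table 7, lists the chemistry item "Glucose (fasting") among the required safety laboratory tests and restricts it to no particular visit.
- **The food rule.** Protocol Section 5.3.1 requires abstinence from food and drink other than water for at least "4 hours prior to any safety laboratory evaluations conducted at pre-AM application". The next bullet reads: "Otherwise, water, meals, and snacks may be consumed without restriction".
- **The sampling days.** Note m to Table 1 of the protocol says: "Safety labs will be collected at screening, admission (D-1), during in-patient dosing as specified in Table 1, at discharge, and at early termination". The marks in the Table 1 row fall on screening, D-1, D5, D7, D10, D12 and early termination.
- **The baseline.** SAP Section 3.1.2 says: "Baseline of safety laboratory tests is defined as the pre-dose measurement on Day -1". If that value is missing, the last pre-dose measurement is used.

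**The concern.** A test named as fasting should be taken under the same food condition at each visit, above all at the visit that serves as baseline. Here the protocol does more than leave the condition open: its second bullet expressly allows food before the Day -1 and Day 12 draws.

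Safety laboratory tests are part of the primary endpoint. The laboratory baseline also has uses beyond any summary table. Protocol Section 8.2.4 has clinically significant abnormal results repeated until they return to normal or baseline, and the adverse event definition in Appendix 3 includes clinically significant results that have worsened from baseline. A baseline glucose taken at an unknown time after a meal is a poor reference for either purpose. A fed Day 12 value could also be mistaken for a change after dosing ended.

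**Working it through.** No power, alpha or event figure bears on this point. The check sets the food rule against the laboratory days and the application days.

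**Application days.** Note d to Table 1 says: "Participants will be admitted at least 12 hours prior to dosing". There is thus no application on Day -1. Note j says: "On D10, study intervention/vehicle will be applied, at AM only". Applications therefore run from D1 to the morning of D10, and D11 and D12 have none.

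| Scheduled safety laboratory | AM application that day? | Within the rule in 5.3.1? |
|---|---|---|
| Screening | No | No |
| D-1 (SAP baseline) | No | No |
| D5 | Yes | Only if drawn before it |
| D7 | Yes | Only if drawn before it |
| D10 | Yes | Only if drawn before it |
| D12 (discharge) | No | No |
| Early termination | Not specified | Nothing places it under the rule |

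**Count.** There are 7 scheduled occasions, and the rule can reach at most 3 (D5, D7, D10). The fairer count leaves out screening, whose laboratory data need not be reported (Protocol 9.3.2), and early termination, which applies only to participants withdrawn early. That leaves 7 − 2 = 5 occasions for a completer. At most 3 are covered, and 5 − 3 = 2 are not: the baseline and the final sample.

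**Fallback baseline.** If the Day -1 value is missing, the only other scheduled pre-dose laboratory sample is the one at screening, which is also outside the rule.

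**Draw time on dosing days.** Notes h, i and n place ECGs, vital signs and PK samples before the morning application on D2, D5 and D7, and refer D1 and D10 to Table 2. Note m gives no such timing for the safety laboratories, and Table 2 has no laboratory row. Fasting on D5, D7 and D10 is therefore likely but not assured.

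**Planned use of the baseline.** SAP 6.1.1.2 says only that laboratory data are listed and summarized by treatment under sponsor standards. Change from baseline is named for vital signs (SAP 6.1.1.3) and ECG (SAP 6.1.1.4), but not for laboratory data. SAP 3.1.2 nevertheless defines a laboratory baseline.

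**The case against.** A reader might infer a definite bias: a fed baseline followed by fasted on-treatment samples would make glucose appear to fall and could hide a real rise. The documents do not support this. The draw time on D5, D7 and D10 is not stated, and Day -1 samples may be fed but need not be. Nor does the SAP name a change-from-baseline summary for laboratory data; any such table would come from sponsor standards that are not among the documents. The abnormality assessment in SAP 3.1.2 also disregards whether the baseline lies within the reference range, so that output is not distorted through baseline status.

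Other points on this side have weight:

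- **Laboratory manual.** Protocol 8.2.4 requires laboratory tests to follow the manual as well as the Schedule of Activities. The manual, or the fasting label itself, may lead the site to fast participants at every draw. That may well happen in practice, but such an instruction would contradict the unrestricted-food sentence in 5.3.1. The protocol can state a general rule when it means one: Section 5.3.3 restricts strenuous exercise before every clinical laboratory blood draw.
- **Limited consequence.** One analyte among more than 30 in Table 7 is affected. The nonclinical target organs are the immune and hematolymphopoietic systems, the risk table names no metabolic risk, and no hypothesis is tested.
- **Vehicle group.** Vehicle participants follow the same schedule, so a meal effect would be expected in both arms. With 4 active and 2 vehicle participants per cohort, however, individual differences in meal timing cannot be relied on to balance. An optional cohort on the same product could add vehicle participants, since the SAP groups vehicle by ointment or cream.

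These points limit the concern to a minor one. They do not remove the conflict between the food rule and the name of the test.

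**Conclusion.** The point holds as a minor inconsistency. On the text, the Day -1 baseline and Day 12 glucose values may be fed although the test is labelled fasting, and fasting on the three dosing days depends on a draw time that is not stated. Any comparison of glucose with the Day -1 value may therefore mix fed and fasted results.

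Its extent is two of a completer's five laboratory days outside the rule, with the other three conditional. The shift in glucose cannot be sized or signed, because it depends on time since the last meal and the documents do not give that. The conclusion rests on reading the Table 1 marks as listed and on no unseen manual settling the matter. It does not extend to other analytes or show that the planned safety conclusions would be wrong.

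**What to change.** Reconcile Section 5.3.1, Table 7 and note m:

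1. In 5.3.1, apply the protocol's existing abstinence period before every scheduled safety laboratory sample: at least D-1, D5, D7, D10 and D12, and screening and early termination where feasible.
2. Exempt unscheduled safety laboratories explicitly. Simply deleting the reference to morning application would extend the fast to samples that Sections 8.2 and 8.2.4 allow at any time for a perceived safety issue.
3. State in note m that the D5, D7 and D10 samples are drawn before the morning application.
4. Record fasting status with each sample, and flag any non-fasted glucose value in listings and summaries.

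The cost is a reworded bullet, an extended footnote, one data field and an instruction to participants. The downside is a few hours without food before the admission and discharge samples.
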